8.18.3. Visit 3 – 6-Months-of-Age Follow-up (Clinic: 160-200 Days After Visit 1)

- Record concomitant medication associated with SAEs.
- Record breastfeeding information.
- Collect a blood sample (approximately 5 mL) for immunogenicity testing. The volume of blood collected will be based on the weight of the infant (refer to [Table 1](#)).
- Record AEs, SAEs, and AESIs as described in [Section 8.3](#).
- Collect e-diary or assist the maternal participant to delete application.
- Complete the source documents.
- The investigator or an authorized designee completes the CRFs.

8.19. COVID-19 Surveillance (All Infant Participants)

If an infant participant experiences any of the following (irrespective of perceived etiology or clinical significance), the maternal participant is instructed to contact the site immediately and, if confirmed, participate in an in-person or telehealth visit as soon as possible, optimally within 3 days after symptom onset (and at the latest 4 days after symptom resolution). Note that this does not substitute for an infant participant's routine medical care. Therefore, maternal participants should be encouraged to seek care, if appropriate, from their infant's usual provider.

Additionally:

- If new symptoms are reported within 4 days after resolution of all previous symptoms, they will be considered as part of a single illness and a second illness visit is not required;
- Surveillance of potential COVID-19 symptoms should continue even if a participant has a positive SARS-CoV-2 test earlier in the study.

Signs and symptoms of an acute respiratory illness in the infant will not be considered a potential COVID-19–related illness if they occur within the first 72 hours after birth and should not trigger an illness visit.

- A diagnosis of COVID-19;
- Fever;
- New or increased cough;
- New or increased shortness of breath;
- Diarrhea;
- Vomiting.

8.19.1. Potential Infant COVID-19/MIS-C Illness Visit (Optimally Within 3 Days After Potential COVID-19 Illness Onset)

This visit may be conducted as an in-person or telehealth visit; a telehealth visit involves the sharing of healthcare information and services via telecommunication technologies (eg, audio, video, videoconferencing software) remotely, thus allowing the parent and investigator to communicate on aspects of the infant's clinical care.

As a participant's COVID-19 illness may evolve over time, several contacts may be required to obtain the following information:

- Record AEs, as appropriate as described in [Section 8.3](#). Note: Potential COVID-19 illnesses that are consistent with the clinical endpoint definition should not be recorded as AEs. These data will be captured as efficacy assessment data only on the relevant pages of the CRF, as these are expected endpoints.
- Record details of any of the prohibited medications specified in [Section 6.5.1](#) received by the participant if required for his/her clinical care.
- If the visit is conducted in person, obtain a nasal swab (collected by site staff). Alternatively, if conducted by telehealth, instruct the maternal participant to collect a nasal swab from the infant and ship for assessment at the central laboratory.
- Collect COVID-19–related standard-of-care clinical and laboratory information. This includes, but is not limited to:
 - Clinical signs at rest indicative of severe systemic illness:
 - RR (breaths/min): >50 in birth to 1 week of age, ≥ 40 in 1 week to 1 month of age, ≥ 34 in 1 month to 6 months of age;
 - HR (beats/min): >180;
 - SpO₂ $\leq 92\%$ on room air or >50% FiO₂ to maintain $\geq 92\%$ or PaO₂/FiO₂ <300 mm Hg;
 - Respiratory failure (defined as needing high-flow oxygen including nasal CPaP/BiPaP, noninvasive ventilation, mechanical ventilation, or ECMO);
 - Evidence of shock or cardiac failure;
 - SBP (mm Hg):
 - <65 from birth to 1 week of age, <75 from 1 week to 1 month of age, <100 from 1 month to 6 months of age;

OR

- Requiring vasoactive drugs to maintain BP in the normal range;
- Significant acute renal failure: serum creatinine >2 times ULN for age or 2-fold increase in baseline creatinine;

- Significant GI/hepatic failure: total bilirubin >4 mg/dL or ALT 2 times ULN for age;
- Significant neurologic dysfunction: Glasgow Coma Scale score <11 or acute change in mental status with a decrease in Glasgow Coma Scale score ≥ 3 points from abnormal baseline;
- Admission to an ICU;
- Death;
- Clinical diagnosis;
- Local laboratory SARS-CoV-2 test result(s). Note that if it is routine practice to perform a repeat local SARS-CoV-2 test for any reason, then a repeat nasal swab should also be obtained and shipped for assessment at the central laboratory.
 - Full blood count, blood chemistry, specifically creatinine, urea, liver function tests, and CRP, ESR, fibrinogen, procalcitonin, D-dimer, ferritin, LDH, or IL-6 if available.
- Number and type of any healthcare contact; duration of hospitalization and ICU stay.

8.19.2. Potential Infant COVID-19 Convalescent Visit (28 to 35 Days After Potential COVID-19 Illness Visit)

- Record AEs, as appropriate as described in [Section 8.3](#). Note: Potential COVID-19 illnesses that are consistent with the clinical endpoint definition should not be recorded as AEs. These data will be captured as efficacy assessment data only on the relevant pages of the CRF, as these are expected endpoints.
- Record details of any of the prohibited medications specified in [Section 6.5.1](#) received by the participant if required for her clinical care.
- Collect a blood sample (up to 5 mL based on weight [[Table 1](#)]) for immunogenicity testing.
- Collect/update COVID-19–related clinical and laboratory information (detailed in [Section 8.13.1](#)).
- Complete the source documents.
- The investigator or an authorized designee completes the CRFs.
- Record any AEs that occur within the 48 hours after the blood draw as described in [Section 8.3](#).

9. STATISTICAL CONSIDERATIONS

Methodology for summary and statistical analyses of the data collected in this study is described here and further detailed in a SAP, which will be maintained by the sponsor. The SAP may modify what is outlined in the protocol where appropriate; however, any major modifications of the primary endpoint definitions or their analyses will also be reflected in a protocol amendment.

9.1. Estimands and Statistical Hypotheses

9.1.1. Estimands

The estimands corresponding to each primary, secondary, and exploratory objective are described in the table in [Section 3](#).

In the primary safety objective evaluations, missing reactogenicity e-diary data will not be imputed. Missing AE start dates will be imputed according to Pfizer safety rules. No other missing information will be imputed in the safety analysis.

The estimands to evaluate the immunogenicity objectives are based on the evaluable immunogenicity populations ([Section 9.3](#)). These estimands estimate the vaccine effect in the hypothetical settings where participants follow the study schedules and protocol requirements as directed. Missing antibody results will not be imputed. Immunogenicity results that are below the LLOQ will be set to $0.5 \times \text{LLOQ}$ in the analysis; this may be adjusted once additional data on the assay characteristics become available.

The estimands to evaluate the efficacy objectives are based on the evaluable efficacy populations ([Section 9.3](#)). These estimands estimate the vaccine effect in the hypothetical setting where participants follow the study schedules and protocol requirements as directed. In addition, VE will also be analyzed by the all-available efficacy (mITT) populations. Missing laboratory results will not be imputed.

9.1.2. Statistical Hypotheses

Due to early enrollment termination and reduced sample size, all endpoints will be analyzed descriptively without formal hypothesis tests.

9.2. Sample Size Determination

The sample size for the Phase 2 portion of the study and for the entire study is not driven by statistical hypothesis testing.

For safety outcomes, [Table 5](#) shows the probability of observing at least 1 AE for a given true event rate of a particular AE, for various sample sizes. For example, if the true AE rate is 2%, with 100 participants in a vaccine group, there is 95% probability of observing at least 1 AE in Phase 2. If the true AE rate is 1%, with 175 participants in a vaccine group, there is 83% probability of observing at least 1 AE in Phase 3.

Table 5. Probability of Observing at Least 1 AE by Assumed True Event Rates With Different Sample Sizes

Assumed True Event Rate of an AE	N=100	N=175
0.1%	0.10	0.16
0.3%	0.26	0.41
0.5%	0.39	0.58
0.8%	0.55	0.75
1.0%	0.63	0.83
2.0%	0.87	0.97
3.0%	0.95	>0.99

Note: N = number of participants in a vaccine group.

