9.4.2. Primary Endpoint(s)

Endpoint	Statistical Analysis Methods
Safety (maternal participants)	Descriptive statistics will be provided for each reactogenicity endpoint for each dose and vaccine group. Local reactions and systemic events from Day 1 through Day 7 after each vaccination (where Day 1 is the day of vaccination) will be presented by severity and cumulatively across severity levels. Descriptive summary statistics will include counts and percentages of participants with the indicated endpoint and the associated Clopper-Pearson 95% CIs (see Section 9.4.1.1).

Endpoint	Statistical Analysis Methods
	
AEs will be categorized according to MedDRA terms. Counts, percentages, and the associated Clopper-Pearson 95% CIs of AEs from Dose 1 to 1 month after Dose 2 will be provided for each vaccine group. A 3-tier approach will be used to summarize AEs in Phase 2/3. Under this approach AEs are classified into 1 of 3 tiers: (1) Tier 1 events are prespecified events of clinical importance and are identified in a list in the product's safety review plan; (2) Tier 2 events are those that are not Tier 1 but are considered "relatively common"; a MedDRA preferred term is defined as a Tier 2 event if there are at least 1% of participants in at least 1 vaccine group reporting the event; and (3) Tier 3 events are those that are neither Tier 1 nor Tier 2 events. Analysis methods are described in Section 9.4.1.1.
 
SAEs will be categorized according to MedDRA terms. Counts, percentages, and the associated Clopper-Pearson 95% CIs of SAEs from Dose 1 through 1 month after delivery will be provided for each vaccine group.
 
AEs and SAEs reported for maternal participants during the open-label follow-up period will be summarized separately.

Immunogenicity in participants without evidence of prior SARS-CoV-2 infection (maternal participants)	
GMR, estimated by the ratio of the geometric mean of SARS-CoV-2 neutralizing titers in pregnant women to nonpregnant women 1 month after Dose 2 will be provided along with associated 2-sided 95% CIs (see Section 9.4.1.2.3). Only participants with no serological or virological evidence (up to 1 month after receipt of the second dose) of past SARS-CoV-2 infection will be included in the analysis.
 
The nonpregnant women will be randomly selected from the female participants from study C4591001 in the same age group as the pregnant women.

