2.2. Study Design

This will be a global Phase 2/3, randomized, placebo-controlled, observer-blind study evaluating the safety, tolerability, and immunogenicity of 30 µg of BNT162b2 or placebo administered in 2 doses, 21 days apart, in approximately 350 healthy pregnant women 18 years of age or older vaccinated at 24 to 34 weeks' gestation. Participants will be randomized 1:1 to receive BNT162b2 or placebo (saline).

The Phase 2 portion of the study will include approximately 200 pregnant women randomized 1:1 to receive BNT162b2 or placebo (saline) at 27 to 34 weeks' gestation. The IRC will review safety data through 7 days after the second dose for all Phase 2 participants.

The Phase 3 portion of this study will include approximately 150 pregnant women at a 1:1 randomization ratio to assess the safety, tolerability, and immunogenicity of BNT162b2 among pregnant women enrolled at 24 to 34 weeks' gestation. Phase 3 will proceed after the first 200 maternal participants have been enrolled in Phase 2.

Maternal participants who originally received placebo will receive BNT162b2 at defined time points as part of the study.

Enrollment in this study was terminated on 25 Oct 2021 with approximately 350 participants enrolled. Enrollment was terminated because of enrollment challenges into a placebo-controlled study as a result of universal recommendations for COVID-19 vaccination of pregnant women and the increased global availability of COVID-19 vaccines. Enrollment numbers within this protocol have been modified accordingly.

The study is observer-blinded, as the physical appearance of the investigational vaccine and the placebo may differ. The participant, investigator, study coordinator, and other site staff will be blinded through the 1-month postdelivery visit for each maternal participant. At the study site, only the dispenser(s)/administrator(s) are unblinded.

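### Protocol Section 9.2 gives a 95% chance of observing a 2% adverse event with 100 women per group; the arithmetic and its own Table 5 give 87%, and the second example's Phase 3 label describes the whole study

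*Protocol*

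**What the plan says.** Protocol Section 9.2 opens with "The sample size for the Phase 2 portion of the study and for the entire study is not driven by statistical hypothesis testing". For safety it relies instead on the probability of seeing at least one case of an adverse event (AE) at an assumed true rate. Table 5 tabulates this for N=100 and N=175, with a footnote defining "N = number of participants in a vaccine group". Two worked examples introduce the table:

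- First: "if the true AE rate is 2%, with 100 participants in a vaccine group, there is 95% probability of observing at least 1 AE". The sentence assigns this to Phase 2.
- Second, for a true rate of 1%: "with 175 participants in a vaccine group, there is 83% probability of observing at least 1 AE in Phase 3".

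Table 5 gives 0.87 for 2.0% at N=100, 0.95 for 3.0% at N=100, and 0.83 for 1.0% at N=175.

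The group sizes come from Protocol Section 4.1, which gives about 200 women in Phase 2, about 150 in Phase 3 and about 350 in all, randomized 1:1. SAP Section 2.2 agrees on Phase 3: "The Phase 3 portion of this study will include approximately 150 pregnant women at a 1:1 randomization ratio".

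**The concern.** The first example contradicts the table it is meant to illustrate. It pairs the 2% rate with the probability that Table 5 shows for 3%.

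The second example has a different fault. Its rate, group size and probability fit together, but 175 per group cannot be Phase 3 when Phase 3 has about 150 women across both groups.

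The first fault matters more. With no hypothesis test in the study, these probabilities are the only quantitative statement in Section 9.2 of what the safety sample can show, and maternal safety is a primary objective. A reader who takes the sentence without checking the table would believe a 2% AE has a 1-in-20 chance of going unseen in a Phase 2 vaccine group. The true chance is closer to 1 in 7.5.

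**Working it through.** **Inputs**

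- First example (Protocol 9.2): rate 2%, n = 100 per group, stated probability 95%.
- Second example (Protocol 9.2): rate 1%, n = 175 per group, stated probability 83%, labelled Phase 3.
- Group sizes (Protocol 4.1, SAP 2.2): Phase 2 is 200/2 = 100; Phase 3 is 150/2 = 75; whole study is 350/2 = 175.

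**Formula.** For independent participants with a common rate p, P(at least 1) = 1 − (1 − p)^n.

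**Step 1: reproduce Table 5.** All 14 cells agree with the printed values.

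| True rate | N=100 computed | N=100 printed | N=175 computed | N=175 printed |
|---|---|---|---|---|
| 0.1% | 0.0952 | 0.10 | 0.1606 | 0.16 |
| 0.3% | 0.2595 | 0.26 | 0.4089 | 0.41 |
| 0.5% | 0.3942 | 0.39 | 0.5841 | 0.58 |
| 0.8% | 0.5521 | 0.55 | 0.7548 | 0.75 |
| 1.0% | 0.6340 | 0.63 | 0.8278 | 0.83 |
| 2.0% | 0.8674 | 0.87 | 0.9709 | 0.97 |
| 3.0% | 0.9524 | 0.95 | 0.9952 | >0.99 |

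The formula is therefore the one the plan used, and the table is sound.

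**Step 2: first example.** 1 − 0.98^100 = 0.8674, or 87%. The stated 95% is 95 − 86.7 = 8.3 percentage points too high. The chance of seeing no case is 0.98^100 = 0.1326, or 13%, against the implied 5%.

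**Step 3: look for a reading that gives 95% at a 2% rate.**

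- Poisson approximation, 1 − exp(−2): 0.8647.
- Both Phase 2 groups pooled, n = 200: 0.9824.
- Whole-study group, n = 175: 0.9709.
- n = 150: 0.9517. This is numerically close, but 150 is the Phase 3 total over both groups, and the sentence specifies 100 in a vaccine group in Phase 2.
- Rate changed to 3%, n = 100: 0.9524, which is the next row of Table 5.

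Nothing gives 95% from the stated inputs.

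As a measure of the gap, 95% at a 2% rate needs ln(0.05)/ln(0.98) = 148.3, so 149 per group. At 100 per group, 95% is reached at a rate of 1 − 0.05^(1/100) = 2.95%. The protocol sets no 95% detection target, so neither figure implies a shortfall in sample size.

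**Step 4: second example.** 1 − 0.99^175 = 0.8278, or 83%, as stated. For Phase 3 alone, 1 − 0.99^75 = 0.5294, or 53%. The number is right for 175 per group; the label is not right for Phase 3.

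**The case against.** The case for leaving this alone is that it has no consequence. The sentence is offered as an example, and the correct value sits in the table it points to. All endpoints are descriptive (Protocol 9.1.2). Enrollment ended on 25 Oct 2021, so no sample-size decision is left to influence. The stopping rules in Section 8.2.3 act on observed events, not detection probabilities, and Phase 3 proceeds once 200 women are enrolled in Phase 2. The SAP does not repeat the example. All of this stands, and it keeps the point minor, but it does not make the sentence correct.

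On the second example, it can fairly be said that the sentence states its own N, that its probability is right for that N, and that the label might loosely mean cumulative through Phase 3. This stands in part: there is no arithmetic error there, and the intended meaning is an inference. The inference is well supported, because 350/2 = 175 and Section 9.2 itself opens by naming the Phase 2 portion and the entire study.

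The documents also do not show whether the rate or the probability was mistyped in the first example. Either correction would be consistent with Table 5.

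**Conclusion.** The concern holds, at minor severity. For a 2% AE with 100 per group, the stated 95% should be 86.7%, so the chance of missing the event in a Phase 2 vaccine group is 13% rather than 5%. The second example's 83% is correct for 175 per group, which is the whole study. Its Phase 3 label is a wording fault; Phase 3 alone would give about 53%.

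These figures assume independent participants, one common true rate, and the planned group sizes of 100, 75 and 175, which the documents give as approximate totals split 1:1. Section 9.2 uses no dropout allowance, and none is used here.

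The error stays within Section 9.2. The maternal safety population takes in all randomized and dosed women (Protocol 9.3, SAP Section 4), so the AE analyses already draw on the whole study. No analysis or decision depends on the misstated figure.

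**What to change.** Make two wording corrections in Protocol Section 9.2:

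1. Restate the first example either as a 2% rate with 87% probability or as a 3% rate with 95% probability, whichever the sponsor intended.
2. In the second example, replace the Phase 3 label with Phases 2 and 3 combined.

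Table 5, the sample size, the analysis sets and the SAP need no change, so the cost is limited to editing these two sentences.

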9.3. Analysis Sets

For purposes of analysis, the following analysis sets are defined:

Population	Description
Enrolled	All participants who have a signed ICD.
Randomized	All participants who are assigned a randomization number in the IWR system.
Evaluable immunogenicity (maternal)	All eligible randomized participants who receive 2 doses of the vaccine to which they are randomized with Dose 2 received within the predefined window, have at least 1 valid and determinate immunogenicity result from the blood sample collected within an appropriate window, and have no other important protocol deviations as determined by the clinician.
Dose 1 evaluable immunogenicity (maternal)	All eligible randomized participants who receive Dose 1 of the vaccine to which they are randomized, have at least 1 valid and determinate immunogenicity result from the blood sample collected after Dose 1 and before Dose 2, and have no other important protocol deviations before Dose 2 as determined by the clinician.
Evaluable immunogenicity (infant)	All infant participants born to evaluable immunogenicity maternal participants and have no important protocol deviations as determined by the clinician.
All-available immunogenicity (maternal)	All participants who receive at least 1 dose of the study intervention with at least 1 valid and determinate immunogenicity result after vaccination.
All-available immunogenicity (infant)	All infant participants born to all-available immunogenicity maternal participants.
Evaluable efficacy (maternal)	All eligible randomized participants who receive all vaccination(s) as randomized within the predefined window and have no other important protocol deviations as determined by the clinician.
All-available efficacy (mITT) (maternal)	Dose 1 all-available efficacy: All randomized participants who receive at least 1 vaccination. Dose 2 all-available efficacy: All randomized participants who complete 2 vaccination doses.
All-available efficacy (mITT) (infant)	All infant participants born to Dose 1 all-available maternal participants.

Population	Description
Safety (maternal)	All randomized participants who receive at least 1 dose of the study intervention.
Safety (infant)	All infant participants born to maternal participants who receive at least 1 dose of the study intervention.

9.4. Statistical Analyses

The SAP will be developed and finalized before any analyses are performed and will describe the analyses and procedures for accounting for missing, unused, and spurious data. This section is a summary of the planned statistical analyses of the primary and secondary endpoints.

9.4.1. General Considerations

CI for all endpoints in the statistical analysis will be presented as 2-sided at the 95% level unless specified otherwise.

The safety analyses are based on the safety populations. Participants will be summarized by vaccine group according to the study intervention they (or their mothers) actually received. Missing reactogenicity e-diary data will not be imputed; missing AE dates will be handled according to the Pfizer safety rules.

For all the immunogenicity endpoints, the analysis will be based on the evaluable immunogenicity populations. An additional analysis may be performed based on the all-available immunogenicity populations if there is a large enough difference in sample size between the all-available immunogenicity populations and the evaluable immunogenicity populations. Participants will be summarized according to the vaccine group to which they (or their mothers) were randomized. Missing serology data will not be imputed.

9.4.1.1. Analyses for Binary Data

Descriptive statistics for categorical variables (eg, proportions) are the percentage (%), the numerator (n) and the denominator (N) used in the percentage calculation, and the 95% CIs where applicable.

The exact 95% CI for binary endpoints for each group will be computed using the F distribution (Clopper-Pearson). The 95% CI for the between-group difference for binary endpoints will be calculated using the Miettinen and Nurminen method.

The 3-tier approach will be used to summarize AEs. For both Tier 1 (if any are identified during the study) and Tier 2 events, a 95% CI for the between-group difference in proportions will be calculated based on the Miettinen and Nurminen method. In addition, for Tier 1 events (if any), the asymptotic p-values will also be presented for the difference in proportions, based on the same test statistic and under the assumption that the test statistic is asymptotically normally distributed. For Tier 3 events, counts and percentages for each vaccine group will be provided.

